6.2.4 Non-serious Adverse Reaction (NSAR)

An adverse reaction that does not meet any of the serious criteria in 6.2.3.

Protocol/Amendment No.: RETRO STUDY, v0.3

VEAP ID NO: 7651

6.2.5 Special Situations

The following special situations are considered important safety information and must be reported, regardless of seriousness or causality, if the investigator becomes aware of them:

- Overdose
- Exposure to product during pregnancy or lactation
- Lack of therapeutic effect
- Off-label use, medication error, misuse, abuse, or occupational exposure
- Suspected transmission via a medicinal product of an infectious agent
- Unexpected Therapeutic Benefit/Effect

6.2.6 Health Outcome of Interest (HOI)

Health Outcomes of Interest (HOIs) are pre-specified clinical events or outcomes that are collected according to the protocol. HOIs may be represented as diagnosis, treatment or procedures. Examples of HOIs include syncope or hypoglycaemia collected as study endpoints. HOIs must be assessed as part of AE collection and may meet criteria for AE reporting. Specifically, the investigator must assess each HOI for serious criteria and causality. If the HOI meets criteria specified in the protocol for AE reporting, then it must be reported as such..

6.2.7 Sponsor's product

Sponsor's product includes any pharmaceutical product, biological product, device, diagnostic agent or protocol-specified procedure, whether investigational (including placebo or active comparator product) or marketed, manufactured by, licensed by, provided by or distributed by the Sponsor for human use.

6.2.8 Causality Assessment

A causality assessment is the determination of whether or not there is at least a reasonable possibility that a product caused the adverse event. Causality must be recorded on the AE form for each reported event in relationship to a Sponsor's product.

Secondary Data Collection

Only AEs with an explicit and definitive notation (by a healthcare provider) of a causal relationship with a product in the medical records or other secondary data being reviewed should be reported as NSAR/SARs. During review of secondary data, causality should never be assigned retrospectively.

6.5 Sponsor Responsibility for Reporting Adverse Events

All adverse events will be reported to regulatory agencies, NRES/IRB/IECs and investigators in accordance with all applicable global laws and regulations.

Protocol/Amendment No.: RETRO STUDY, v0.3

VEAP ID NO: 7651

7 Product Quality Complaint Reporting

Although product quality complaints are not actively solicited in this study, there are certain circumstances in which individual Product Quality Complaints (PQCs) will be reported. For example, during review of medical records or physician notes (paper or electronic), to collect data as required by the protocol, if a notation of a PQC to any MSD product is identified, the PQC must be reported by the study investigator or qualified designee using the Product Quality Complaint (PQC) Reporting Form following the instructions in Table 2. The PQC Reporting Form must be fully completed in English. Once the PQC Reporting Form is submitted, the investigator or designee may be contacted for further information.

If both an AE and a PQC occur, the AE should be reported according to the AE reporting requirements in the protocol and the PQC should be reported per Table 2.

EVENT TYPE	INVESTIGATOR TIMEFRAME	
	Investigator to MSD	
PQC	24 hours from receipt	
PQC reports must be submitted via e-mail by the investigator to the local designated point of contact (DPOC) using a PQC form.		
Submitting PQC reports to MSD: All PQCs must be submitted to the local DPOC in English using a PQC form (attached) via secure (password protected) email to [contact]		

7.1 DEFINITIONS

7.1.1 Product Quality Complaint (PQC).

Any communication that describes a potential defect related to the identity, strength, quality, purity or performance of a product identified by an external customer. This includes potential device or device component malfunctions.

7.1.2 Malfunction

The failure of a device (including the device component of a combination product) to meet its performance specifications or otherwise perform as intended. Performance specifications include all claims made in the labeling for the device.

Protocol/Amendment No.: RETRO STUDY, v0.3

VEAP ID NO: 7651

8 Statistical Analysis Plan

Detailed description of the statistical analyses, any deviation from the protocol, and assumptions employed will be presented in a detailed Statistical Analysis Plan (SAP) that will be prepared prior to database closure and initiation of any statistical analyses.

All analyses will be conducted on the per protocol population unless otherwise stated in the sections below. Missing data will not be imputed, and all analyses will be based on observed data only.

8.1 Statistical Methods

8.1.1 Primary Objective(s):

a) Demographics and description of RAL OD patients

The demographic characteristics of all subjects starting RAL OD (Gender; menopausal status, Age, Ethnicity) will be presented as summary statistics (mean, median, standard deviation, IQR, maximum, minimum and for continuous measurements and numbers and proportions for categorical measurements)

b) Clinical and treatment characteristics (co-morbidities, co-medications, baseline ART) Clinical and treatment characteristics of all subjects initiating treatment with RAL OD will be analysed descriptively using summary statistics. These will include the mean, median, standard deviation, and 95% confidence interval of the mean for continuous variables and frequency distributions for categorical variables.

8.1.2 Secondary objectives

a) Clinical and treatment characteristics (co-morbidities, co-medications, ART, discontinuations)

Clinical and treatment characteristics and changes from baseline in all subjects who have data available at the follow up appointment will be analysed descriptively using summary statistics. These will include the mean, median, standard deviation, and 95% confidence interval of the mean for continuous variables and frequency distributions for categorical variables.

b) Virologic and immunologic outcomes

Virologic and immunologic outcomes will be analysed descriptively at baseline and follow up appointment. Test results closest to the 6 month time point will be used for these analyses.

Frequency and proportion of patients with virologic suppression (Section 3.1) at baseline and 6 months will be described.

Among the virologically suppressed patients at baseline, frequency and proportion of patients with sustained virologic suppression, and viral load measures (Section 3.1) at 6

Protocol/Amendment No.: RETRO STUDY, v0.3

VEAP ID NO: 7651

months will be described. Data will be presented as the mean, median, interval of the mean for continuous variables and frequency distributions for categorical variables. A mean change from RAL OD initiation in CD4 cell count will be described at the 6 month time point.

Per Protocol Analysis: Primary Objective = All subjects who initiated RAL OD treatment.

Secondary Objective: Numerator = patients who remained on RAL OD treatment for the 6 month study period; Denominator = all patients who initiated RAL OD therapy.

8.2 Bias

It is intended that data will be collected on consecutive patients in who at least 6 months follow-up was possible (i.e. started RAL OD during or after September 2017). Eligible patients must have completed their 6 month follow up before 31st December 2018. This will include any patients who may have moved treatment centres since initiation. Participating centres will be selected to be representative of the UK population, one site from within London (where approximately 50% of HIV patients in the UK are currently treated) and one from outside London will be used.

The study is a retrospective chart review study that will be using data extracted from databases; any missing data will be queried with the sites and if not available, will be recorded as such.

Any observational study has the possibility of residual confounding due to unknown risk factors [13]. However this study is designed to collect information on recent prescribing practice and is based on clinical experience and knowledge of the HIV physician.

8.2.1 Methods to Minimize Bias

By including 2 treatment centres we hope to reduce single centre bias. Furthermore, to minimise bias and to ensure a sample population which is representative of UK, site selection will be based on treatment hubs within areas of high prevalence.

As approximately 50% of UK HIV patients are treated in London one of these treatment centres will be randomly selected from the 6 largest treatment centres in London. The other treatment centre will be a non-London centre.

Patients who from September 2017 were initiated on RAL OD for at least 6 months and who completed their 6 month follow up before 31st December 2018, up to 150 patients per site initially, will be selected sequentially to minimise bias. Should the larger site continue to recruit additional patients in order to meet the target of 300, the same methods will be used.

Protocol/Amendment No.: RETRO STUDY, v0.3

VEAP ID NO: 7651

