Vendor/Collaborator	Adelphi Real World Ltd	
Rationale	This study will provide data on patient characteristics and treatment patterns of HIV positive patients initiating raltegravir 1200mg once daily (RAL OD) (2 x 600mg). There is a lack of published real world data on the use of once daily raltegravir, and these data will show how RAL OD is used in the real world setting in the UK.	
Primary Objective	To describe and understand the real world utilisation of RAL OD.	
Primary Outcome measures	Description of patient demographics (age, gender, and ethnicity), baseline clinical and treatment characteristics (co-morbidities, co-medications, AIDS defining illnesses within the last 6 months/ever) in ART naïve and experienced HIV-1 infected adult subjects. Description of Antiretroviral therapy (ART) treatment combination initiated with RAL OD. If treatment experienced, description of prior ART regimen. Description of clinical and treatment characteristics (co-morbidities, co-medications) of subjects who remain on RAL OD at the 6 month time point. Description of any change in clinical and treatment characteristics from baseline to 6 months in subjects who	
Secondary Data Collection Objective	remain on treatment Laboratory parameters at baseline and 6 months (HIV viral load, CD4 cell count), RAL OD discontinuations at 6 months	
Study Design	Non-interventional, observational, multi-centre, retrospective chart review study	
Study Population	HIV-1 infected adults initiating RAL OD as part of their ART at treatment centres within the UK from September 2017	
Study Duration	The study duration is expected to be 6-12 months. Patient data will be collected on all patients starting RAL OD from September 2017 who return for their 6 month (-1/+3 months window) follow up appointment. Eligible patients	

Protocol/Amendment No.: RETRO STUDY, v0.3

VEAP ID NO: 7651

	must have completed their 6 month follow up before 31st		
	December 2018		
Exposure and Outcome	Exposure: RAL OD based ART		
	Outcomes: descriptive utilisation and treatment patterns.		
	Clinical measures (HIV viral load and CD4 cell counts)		
	will be captured as secondary endpoints.		
Statistical Methods	The profile of HIV-1 positive subjects initiating treatment		
	with RAL OD will be analysed descriptively using		
	summary statistics.		
Sample Size and Power	Sample size of 300 across 2 centres. This is large enough		
Calculations	to provide precise estimates overall and allow sub-group		

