3 METHODOLOGY

3.1 Summary of Study Design

This is a non-interventional, retrospective observational chart review study at 2 UK treatment centres that will utilize electronic data capture (EDC) to address study objectives.

The study will capture data from 300 HIV-1 positive adult subjects receiving RAL OD as part of their ART at UK NHS treatment centres. NHS records generally capture all of the usual care of an HIV positive patient including their physical exams, diagnoses, laboratory findings, medication prescriptions, co-morbidities, social history and demographic data.

All eligible HIV-1 infected adult patients (\geq 18 years) who initiated RAL OD based ART from September 2017 will be included in this study on a sequential sampling basis. Data from eligible patients' medical charts will be extracted for the time of initiation and at 6 months (window of -1/+3 months) post-initiation follow up appointment.

The index ARV regimen is defined as the first RAL 1200mg OD (2 x 600mg) containing ARV regimen a patient receives and the baseline will be defined as the RAL 1200mg OD

Protocol/Amendment No.: RETRO STUDY, v0.3

VEAP ID NO: 7651

initiation prescription date. Treatment with RAL OD must have been initiated during or after September 2017 and before April 1st 2018 for the primary baseline data collection. Subjects should have at least one 6 month (-1/+3 months) follow up appointment before December 31st 2018 to ensure 6 month secondary outcomes data are available for analysis. Chart review will only be carried out once a patient has completed the 6 month visit to ensure all data are captured retrospectively.

This time period was selected based on expectations of RAL OD utilization over time in the post-launch period and standard UK practice of 6-monthly clinic appointments.

The final analysis will be conducted following database lock after the last study participant has reached the 6 (-1/+3) months treatment milestone, by December 31st^h 2018, and all data queries have been resolved.

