3.2 Study Population

The study will be conducted in 2 NHS hospital HIV departments in the UK. To ensure the data are representative of the UK, centres will be chosen to represent London and non-London in proportion with the treated patient population. As approximately 50% of UK HIV patients are treated in London, one of the potential sites will be selected from the largest treatment centres in London. The additional site will be a non-London treatment centre, and will be selected primarily based on the number of eligible patients treated.

Patients who were initiated on RAL OD at least 6 months ago will be identified by the clinician, Principal Investigator or a member of the clinical team, from review of hospital records and databases as appropriate at each centre. From a list of eligible patients with the required data, the earliest recent record will be recorded as the first participant and then all further eligible participants up to 150 per centre will be selected sequentially to minimize bias.

It is intended that approximately 150 patients will be included from each participating centre to represent a proportionate spread. Oversampling may be performed in the larger centre in order to maintain an overall sample size of 300.

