4.1 Exposure

Subjects treated with RAL OD will be identified by the administering clinicians within the treatment centres. Unless they discontinue treatment during the study period, subjects will have been taking RAL OD for at least 6 months.

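### Entry requires a completed 6-month visit, so initiators without one are never charted, the all-initiator denominator cannot be obtained, and persistence is probably overstated

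*Protocol*

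**What the plan says.** Five places in the protocol make entry depend on something that happens after RAL OD is started:

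- Synopsis, Study Duration: data are collected on patients "who return for their 6 month (-1/+3 months window) follow up appointment".
- Section 3.1: "Chart review will only be carried out once a patient has completed the 6 month visit".
- Section 3.2: the sequential sample is drawn "From a list of eligible patients with the required data".
- Section 8.2: the sample is described as "consecutive patients in who at least 6 months follow-up was possible", but the section then requires eligible patients to have finished that follow-up before the end of 2018.
- Section 8.2.1: patients are those who "were initiated on RAL OD for at least 6 months and who completed their 6 month follow up", with the same end-2018 limit.

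Other places describe a different population. Section 3.3 asks only for HIV-1 infection, adult age and initiation within the stated dates. Section 8.1.2 sets the primary analysis on all subjects who started RAL OD. For the secondary objective, its numerator is patients who stayed on RAL OD for the 6 months, with "Denominator = all patients who initiated RAL OD therapy". Section 2.2 lists the proportion still taking RAL OD and the proportion discontinuing it, and also asks for the regimens of patients who switch. Section 4.1 allows for discontinuers: "Unless they discontinue treatment during the study period".

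**The concern.** The quantity to be reported and the people to be sampled do not match. Whether a patient attends at 6 months is not known at the index date and may well depend on how treatment went. A patient who died, or who stopped and left care, has no visit and so no extracted chart. Sequential selection, which 8.2.1 offers against bias, acts only within the group that returned.

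Two results are exposed. The first is persistence (the proportion still on RAL OD) and its complement, which 8.1.2 expresses over all initiators. The second is the baseline profile, the primary objective, which is meant to show to whom RAL OD is prescribed but would cover only those who came back. A later analysis plan cannot repair either result, because the missing charts are never extracted. The limitations in the synopsis and in 8.2.3 mention missing data, non-random sampling and transcription error, but not this selection.

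**Working it through.** **Plan's own figures.** The only relevant one is the sample size of 300, which is 2 × 150. The protocol gives no attendance, persistence or discontinuation rate, so there is no stated result to reproduce, and the rates below are assumptions.

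**Inputs.**
- A = persistence among attenders, assumed 90%.
- r = share of initiators with no visit in the window, assumed 5%, 10% or 15%.
- q = share of those non-attenders who are still on RAL OD, unknown, varied from 0 to 90%.

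**Formulas.**
- Persistence among all initiators = (1 − r) × A + r × q.
- Overstatement when only attenders are charted = A − [(1 − r) × A + r × q] = r × (A − q).

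**Results: persistence among all initiators (overstatement in points).**

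| r | q = 0 | q = 50% | q = 90% |
|---|---|---|---|
| 5% | 85.5% (4.5) | 88.0% (2.0) | 90.0% (0) |
| 10% | 81.0% (9.0) | 86.0% (4.0) | 90.0% (0) |
| 15% | 76.5% (13.5) | 84.0% (6.0) | 90.0% (0) |

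For example, with r = 10% and q = 0, 0.90 × 0.90 = 0.810, so a reported 90% is 9.0 points too high. If q exceeded 90% the sign would reverse.

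**Initiators behind 300 charted attenders.** 300 / (1 − r) gives 316, 334 and 353 after rounding up, so about 16, 34 or 53 initiators are never seen.

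**Comparison with sampling error.** At n = 300 and p = 0.90 the 95% half-width is 1.96 × √(0.90 × 0.10 / 300) = 3.4 points. With q = 0 the bias exceeds this at every r shown. With q = 50% it exceeds it at r = 10% and 15%. A confidence interval would not reveal it.

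**Baseline profile.** By the same algebra, a baseline proportion shifts by r × (value in attenders − value in non-attenders). The protocol gives nothing from which to put a number on that difference.

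**Dates, for the remedy.** The window is −1/+3 months, so it closes 9 months after initiation.
- Under 3.1 (initiation before 1 April 2018), the last starter, on 31 March, reaches 9 months on 31 December 2018, right at the limit.
- Under 3.3 (before 30 April 2018), the last starter, on 29 April, reaches 9 months on 29 January 2019. That is after the limit and after the mid-January 2019 abstract submission in section 10.

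**The case against.** The strongest reply is that the protocol plainly expects discontinuers. The synopsis lists discontinuations at 6 months, 2.2 asks for subsequent regimens, 4.1 allows for patients who stop, and 8.1.2(a) names discontinuations among the characteristics to be summarised. That stands: a patient who stops or switches but attends is in the sample.

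A reader might infer from the duration phrase in 8.2.1 that discontinuation is zero and persistence 100% by construction. The documents do not support that as the design. The parallel sentence in 3.2 speaks of patients who started at least 6 months ago, and the literal reading would leave objectives in 2.2 empty. The phrase is best treated as a contradiction to be corrected.

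Three further points hold in part:
- Section 2.2 and 8.1.2(a) already restrict several 6-month summaries to patients with data, so the suppression proportions and the switch description are not presented as all-initiator results. This does not rescue the denominator in 8.1.2 or the primary population.
- Section 8.2 expressly includes patients who moved centre, so it would be wrong to say that transfers are never charted. They remain subject to the completed-follow-up condition.
- Missing a visit is not the same as stopping treatment, and the window is wide. The bias could therefore be small, but nothing in the protocol shows that non-attenders persist as well as attenders.

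Completed follow-up might also be read as elapsed time. The synopsis and 3.1, which speak of returning for and completing a visit, do not allow that.

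**Conclusion.** The point holds for initiators with no 6-month visit. As written, the plan cannot deliver the all-initiator denominator in 8.1.2, and it limits the baseline profile to returners. Persistence is biased upward, and discontinuation downward, unless non-attenders persist at least as often as attenders.

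With 90% persistence among attenders and 5% to 15% non-attendance, the overstatement is 4.5 to 13.5 points in the extreme case where every non-attender is off drug. It falls in proportion as their persistence rises, and reaches zero at 90%. All these rates are assumed, and the true size cannot be fixed from the document. The study is descriptive and persistence is a secondary outcome, but it is a named outcome whose stated denominator would be wrong, and the limitations do not disclose this.

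**What to change.** 1. Reconcile the initiation cut-off first (3.1 against 3.3), so that the 9-month window closes by 31 December 2018 for every patient sampled. If the later cut-off is kept, the follow-up limit and the reporting dates must move with it.
2. Define eligibility by facts known at the index date (HIV-1, adult age, first RAL OD prescription within the initiation window, and the existing exclusions) plus follow-up being administratively possible, as the opening of 8.2 already implies.
3. Remove the completed-visit, data-availability and six-month-duration conditions from the synopsis, 3.1, 3.2, 8.2 and 8.2.1, so that they agree with 2.2, 3.3, 4.1 and 8.1.2.
4. Chart consecutive initiators once the visit window has closed, whether or not a visit took place.
5. Report 6-month status over all initiators as on RAL OD, discontinued, transferred, died, or no visit in window. Label laboratory summaries as being among those with data, and give the number without.

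The cost is protocol wording and baseline-only extraction for initiators without a visit. The small downside is that some of the 300 charts will lack 6-month laboratory values.

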8.2.3 Limitations

The results of the study must be interpreted in consideration of the known limitations of chart review studies. Specifically, the use of data extracted from medical charts carries a possibility of information bias related to the validity of the data reported by the service providers, including missing, inconsistent or erroneous information, and the likelihood of human error during transcription.

Furthermore, given that the current study is a retrospective study that will be using data extracted from medical charts, it will not be possible to retrieve any missing data. However, cross-validation will be performed and erroneous data will be clarified with the physicians or delegates.

